## **12. Local Number of Participants**

We will enroll 50 healthy adults aged 18 years or more from the general community with the help of flyers that will be placed at various places at the Emory campus. There will be no exclusion of subjects based on gender or ethnicity.

## **13. Recruitment Methods**

Participants will be recruited through flyers and consent will be obtained during their scheduled study visit. Recruited subjects will not require any follow up visits or additional testing.

## **14. Withdrawal of Participants**

Subjects will only be withdrawn from the study if they are unable to complete the sweat sample collection. After a subject has been withdrawn, the study team will discard incomplete sweat sample collection and no more data will be collected.

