## 2. Objectives

The main objective of this study is to demonstrate the safety and feasibility of using pilocarpine microneedles for sweat induction during the process of sweat testing in healthy human adult subjects ( $\geq 18$  years of age) and comparing it to the standard method of sweat induction (Pilocarpine iontophoresis) in terms of sweat volume collected and sweat chloride concentrations.

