#### 4. Study Design

This is a cross sectional pilot study which will be conducted in a phased manner (Figure 4). The first phase of the study will include the enrollment of 10 healthy adult subjects who will undergo testing to assess the safety and efficacy of pilocarpine microneedle patch. The safety data from the first 10 subjects will be submitted to the Data and Safety Monitoring Board (DSMB) that will review the reported adverse events during testing. The DSMB will independently assess this safety data and provide their recommendations on whether it is safe to continue the study or not. These recommendations will be submitted to the Emory IRB. If there are no safety concerns reported by DSMB, then the second phase of the study will begin where the study team will continue enrollment of an additional 40 subjects to complete testing. After the enrollment and testing of 50 subjects, the study will be completed and another report of safety data will be submitted to the DSMB at the end of the study. The DSMB will review this final report and their final recommendations will be shared with Emory IRB and study team.

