## **7. Procedures Involved**

Informed consent will be obtained by an IRB-approved member of the study staff. The process of informed consent will begin with a verbal description of the experimental tasks. Participants will then have an opportunity to read the informed consent form that explains in more detail the requirements for participation, including protections of privacy and confidentiality. Participants will be told of their rights to discontinue participation at any time and that there will be no immediate benefit to participating and no disadvantage to discontinuing. Participants will be given contact numbers for the PI and the Executive Director of the Human Research Protection Office should they have

any questions or concerns regarding their participation. Informed consent documentation will take place in a private setting convenient to the participant.

Once the consent is obtained, the patient will undergo sweat testing. The testing will be performed with the subject resting comfortably on a chair and total duration of testing will be 45 minutes. The right forearm will be used for pilocarpine iontophoresis and the left forearm will be used for microneedle-based stimulation for a period of 5 minutes. A control microneedle patch without pilocarpine will also be placed on the left forearm to assess for any microneedle patch related changes. After the stimulation phase, collection of sweat will be performed on each forearm simultaneously for a period of 30 minutes (excluding the control microneedle patch site). At the end of the 30-minute sweat collection period, the collection device will be removed and the study visit will be completed. All the collected sweat samples (2 for each subject) will be frozen for later analysis of the sweat volume and chloride concentration.

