## **15. Risks to Participants**

There are some risks associated with both forms of sweat testing.

All study subjects will be warned about the potential risk of skin burns that can occur with the use of the pilocarpine iontophoresis step during the standard-of-care method of sweat testing.

The product insert from the manufacturer detailing this side effect has been added as Appendix 10. This risk is estimated to occur at a rate of about 1 in 50,000 tests. The burns have been reported to be ranging from “tiny black pinholes in the skin” to “crater-like, third degree burns two to three millimeters in diameter”. As per the manufacturer’s product insert, individuals who had these burns had no signs of pain or discomfort during iontophoresis, and the burns are not noticed until after the electrodes are removed. The burns are reported to heal completely in 1-2 weeks with little or no scarring. The manufacturer of pilocarpine iontophoresis also warns about the risk of redness of skin at the electrode site, and in some cases, blister-like welts may form which can persist up to 2-3 hours. However, this standard-of-care method has been approved for use in humans by the FDA.

With the use of pilocarpine microneedle patch, there is a risk of skin irritation or redness that can last for hours after the completion of testing. There is no risk of burns with the pilocarpine microneedle patch. There is no risk of systemic side effects from the exposure to Pilocarpine as the total dose of pilocarpine in each microneedle patch is less than 10% (one-tenth) of the standard adult dose that is used in clinical practice (see section on Pilocarpine doses above on page 8). Not all the pilocarpine that is present on a microneedle patch will be delivered into the skin, and only a fraction of that small dose penetrating the skin may be absorbed into systemic circulation.

Due to the pilot nature of this study, the study will have a Data and Safety Monitoring Board (DSMB) comprised of 3 members that are not affiliated with this study who will review the safety data for the first 10 subjects enrolled. The DSMB charter has been reviewed and signed off on by all the members of the DSMB (Appendix 11).

After the DSMB has reviewed the safety of the pilocarpine microneedle approach in the first 10 subjects, it will provide its recommendations to the study team and this communication will be submitted to Emory IRB as well. If the DSMB recommends

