continuation of the study, then further enrollment will be continued to enroll an additional 40 subjects with close monitoring for any unforeseen risks or side effects of the interventions related to this study in the remaining participants. Any unforeseen side effects of the pilocarpine microneedle patch will be reported to the DSMB for review. The DSMB will again review the safety data at the end of the enrollment of the additional 40 subjects to ensure that no additional concerns have arisen during the remainder of the study. The DSMB will provide their recommendations and summary regarding the safety of the pilocarpine microneedle patch being test in this study and this will also be shared with Emory IRB. If there are any safety concerns reported by the DSMB, then these will be addressed by the study team with an appropriate modification of the study design or intervention. This will be followed by submission of an amended study protocol to the IRB to reflect the changes made to the study protocol. After approval of the amended study protocol, the study team will conduct the revised testing procedure on 10 subjects and submit safety data to the DSMB again for their review and approval.

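### Section 14 ends all data collection, with no exception for safety, once a subject cannot complete sweat collection; this conflicts with the safety objective and the DSMB review

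*Combined protocol and SAP*

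**What the plan says.** Section 14 consists of two sentences. The first sets the only ground for withdrawal: "Subjects will only be withdrawn from the study if they are unable to complete the sweat sample collection". The second sets the consequence: "After a subject has been withdrawn, the study team will discard incomplete sweat sample collection and no more data will be collected". The section does not define inability to complete, ask for the reason, mention the sample from the other forearm, or make an exception for safety data.

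Other sections bear on this:

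- **Section 2:** "The main objective of this study is to demonstrate the safety and feasibility of using pilocarpine microneedles for sweat induction".
- **Section 4:** "The safety data from the first 10 subjects will be submitted to the Data and Safety Monitoring Board", and the board then advises whether it is safe to go on to the next 40.
- **Section 15:** describes the board as three unaffiliated members "who will review the safety data for the first 10 subjects enrolled", so the review set is those enrolled, not those who completed. It adds: "Any unforeseen side effects of the pilocarpine microneedle patch will be reported to the DSMB for review".
- **Section 7:** 5 minutes of stimulation, then 30 minutes of simultaneous collection on both forearms. "At the end of the 30-minute sweat collection period, the collection device will be removed and the study visit will be completed". Also: "All the collected sweat samples (2 for each subject) will be frozen for later analysis of the sweat volume and chloride concentration".
- **Section 6:** photographs of each skin site before and after the interventions.
- **Sections 8 and 24:** every used patch is assayed for pilocarpine.
- **Sections 10 and 13:** one visit of 45 minutes and no follow-up for anyone.

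**The concern.** Section 7 defines collection by time, so a subject who cannot complete it is most naturally one who stops before 30 minutes. Discomfort or a skin reaction is a plausible reason. Such a subject is among the most informative for safety, and Section 14 ends their observation. The stop is also a feasibility result in its own right, yet nothing requires the reason, the forearm or the minutes reached to be recorded.

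Two things are at stake. One is whether the DSMB sees complete safety data for all 10 subjects on whom its first recommendation rests. The other is whether the study can say how often, and for which method, collection could not be finished.

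**Working it through.** **Figure in the plan.** Enrolment is 10 in the first phase plus 40 in the second: 10 + 40 = 50, as stated. The documents give no early-stop rate, adverse-event rate or power calculation, so the point rests on the text and the figures below only show scale.

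**Step 1: the provisions side by side.**

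| Provision | Requires | Section 14 as written |
|---|---|---|
| Section 2 | Safety and feasibility shown | No further data; early stop not characterised |
| Sections 4 and 15 | Safety data on the first 10 enrolled to the DSMB | A withdrawn subject stays among the 10, with observation cut short |
| Section 15 | Unforeseen patch effects reported | Nothing collected after withdrawal that could be reported |
| Section 6 | Photographs after the interventions | Not taken if still outstanding at withdrawal |
| Sections 8 and 24 | All used patches assayed | Not stated whether the assay counts as further data |

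The first three rows conflict. The last two are ambiguous and need only a clarifying sentence.

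**Step 2: what is lost.** Section 14 looks forward and discards only the sweat sample. An event recorded before withdrawal therefore remains. What can be lost is:

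- anything first seen in the rest of the visit, including the skin check when the collector comes off and any photographs not yet taken;
- the volume in the discarded sample, which cannot be recovered because volume is measured later from frozen samples;
- why, when and on which forearm collection failed.

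**Step 3: how much time.** Section 7 schedules nothing after the collector is removed. For a stop at minute m of collection, scheduled time left = 30 − m:

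- m = 5: 25 minutes
- m = 15: 15 minutes
- m = 25: 5 minutes

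The visit is 45 minutes and the scheduled steps take 5 + 30 = 35, leaving 10 unallocated. If all 10 fell after collection, the limits would be 35, 25 and 15 minutes, but the documents do not place them there.

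**Step 4: effect on the first DSMB review (assumed events).** The exact one-sided 95% upper bound for x events in n solves P(X ≤ x | n, p) = 0.05. For x = 0 this is 1 − 0.05^(1/n).

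- 0/10: 1 − 0.05^(1/10) = 25.9%
- 1/10: 39.4%
- 2/10: 50.7%

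If one reaction among the 10 first appeared after an early stop and went unrecorded, the board would see 0/10 (26%) instead of 1/10 (39%). With two, it would see 0/10 instead of 2/10 (51%).

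**Step 5: effect on the paired volume comparison.** If 1, 2 or 5 of 50 stop early (assumed), 49, 48 or 45 full pairs remain. With no stated power target, that loss of numbers is minor.

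**The case against.** The strongest reply is that real harm needs a chain of events. A reaction that makes someone stop is known before withdrawal and is not erased. For the DSMB to miss one, a new reaction would have to appear after the stop, within the same visit, and staff would have to leave it unrecorded despite Section 15. Most of this stands, and it is why the size is put in minutes and the upper bounds are only an illustration. It does not remove the conflict. The Section 15 reporting duty covers unforeseen effects of the patch, whereas irritation and redness are foreseen there, and a duty to report cannot supply observations that Section 14 says not to make.

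Other points also stand. The photographs may be due right after the 5-minute stimulation, since the control site has no collection phase. Iontophoresis burns, noticed when the electrodes come off, would be seen before collection begins. Assaying a patch already used need not count as new data from the subject. A shortened sample is not comparable with a 30-minute volume, so leaving it out of the primary comparison is defensible. The DSMB charter (Appendix 11) is not supplied and may already deal with this.

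A reader might infer three stronger claims that the documents do not support:

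- **That Section 14 erases the adverse event that caused the stop.** It discards only the sample.
- **That Section 14 is why reactions lasting hours are missed.** Nobody is followed after the visit, so these are missed for all subjects.
- **That dry or low-volume sites are dropped, biasing the volume comparison towards the method that fails more often.** That requires treating a full 30-minute collection with little sweat as incomplete, whereas Section 7 defines collection by time. The possibility justifies one clarifying sentence but not a bias estimate.

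**Conclusion.** The concern holds in bounded form. Section 14 states a rule that, followed literally, stops safety recording for part of the only visit in subjects who cannot finish collection. It also leaves a feasibility failure uncharacterised. No supplied section provides an exception, and the rule must be reconciled with Sections 2, 4 and 15.

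The observation lost per subject is about 25, 15 or 5 scheduled minutes for a stop at minute 5, 15 or 25. The change from 26% to 39% in the upper bound assumes exactly one reaction among the first 10, arising after an early stop and entirely unrecorded. How often that would happen cannot be judged from the documents. The conclusion also assumes that the DSMB charter contains no overriding rule. The case for acting rests on the plain conflict, the small size of the first review set and the very low cost of correction, not on a demonstrated large effect.

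**What to change.** Amend Section 14 as follows.

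1. Unless the subject withdraws consent, adverse-event recording and the planned skin photographs continue to the end of the visit after an incomplete collection, and the subject stays in the safety set sent to the DSMB.
2. Also subject to consent, the reason, forearm and minutes collected are recorded, and incomplete collections are counted by method as a feasibility result.
3. A full 30-minute collection is complete whatever its volume, so low and zero volumes enter the paired comparison.
4. Shortened collections may be left out of the primary 30-minute volume comparison but are reported. The used patch is still assayed under Sections 8 and 24.
5. If the DSMB charter already covers any of this, cite it in Section 14.

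The cost is protocol wording and a few data fields, with no extra subjects, visits or procedures. The patch result may look slightly less favourable. Zero volumes cannot be log-transformed, so if any occur the paired summary would need to be untransformed or rank-based.

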## **15. Risks to Participants**

There are some risks associated with both forms of sweat testing.

All study subjects will be warned about the potential risk of skin burns that can occur with the use of the pilocarpine iontophoresis step during the standard-of-care method of sweat testing.

The product insert from the manufacturer detailing this side effect has been added as Appendix 10. This risk is estimated to occur at a rate of about 1 in 50,000 tests. The burns have been reported to be ranging from “tiny black pinholes in the skin” to “crater-like, third degree burns two to three millimeters in diameter”. As per the manufacturer’s product insert, individuals who had these burns had no signs of pain or discomfort during iontophoresis, and the burns are not noticed until after the electrodes are removed. The burns are reported to heal completely in 1-2 weeks with little or no scarring. The manufacturer of pilocarpine iontophoresis also warns about the risk of redness of skin at the electrode site, and in some cases, blister-like welts may form which can persist up to 2-3 hours. However, this standard-of-care method has been approved for use in humans by the FDA.

With the use of pilocarpine microneedle patch, there is a risk of skin irritation or redness that can last for hours after the completion of testing. There is no risk of burns with the pilocarpine microneedle patch. There is no risk of systemic side effects from the exposure to Pilocarpine as the total dose of pilocarpine in each microneedle patch is less than 10% (one-tenth) of the standard adult dose that is used in clinical practice (see section on Pilocarpine doses above on page 8). Not all the pilocarpine that is present on a microneedle patch will be delivered into the skin, and only a fraction of that small dose penetrating the skin may be absorbed into systemic circulation.

Due to the pilot nature of this study, the study will have a Data and Safety Monitoring Board (DSMB) comprised of 3 members that are not affiliated with this study who will review the safety data for the first 10 subjects enrolled. The DSMB charter has been reviewed and signed off on by all the members of the DSMB (Appendix 11).

After the DSMB has reviewed the safety of the pilocarpine microneedle approach in the first 10 subjects, it will provide its recommendations to the study team and this communication will be submitted to Emory IRB as well. If the DSMB recommends

continuation of the study, then further enrollment will be continued to enroll an additional 40 subjects with close monitoring for any unforeseen risks or side effects of the interventions related to this study in the remaining participants. Any unforeseen side effects of the pilocarpine microneedle patch will be reported to the DSMB for review. The DSMB will again review the safety data at the end of the enrollment of the additional 40 subjects to ensure that no additional concerns have arisen during the remainder of the study. The DSMB will provide their recommendations and summary regarding the safety of the pilocarpine microneedle patch being test in this study and this will also be shared with Emory IRB. If there are any safety concerns reported by the DSMB, then these will be addressed by the study team with an appropriate modification of the study design or intervention. This will be followed by submission of an amended study protocol to the IRB to reflect the changes made to the study protocol. After approval of the amended study protocol, the study team will conduct the revised testing procedure on 10 subjects and submit safety data to the DSMB again for their review and approval.

## **16. Potential Benefits to Participants**

- 16.1 There is no direct benefit to the subjects from participation in this study.
- 16.2 The study will benefit the advancement of medical knowledge about the usefulness of pilocarpine microneedle patches for the induction of sweating during the procedure of sweat testing.

## **17. Compensation to Participants**

Subjects will not be compensated for participating in this study.

## **18. Data Management and Confidentiality**

Descriptive analysis will be conducted for the study participants to describe their clinical presentation and long-term outcomes. Several steps will be taken to secure the data by ensuring adequate training of the study team members, authorization of access to the study team for the clinical data, password protection, encryption, and separation of identifiers and data during the storage, use, and transmission. Data will be stored on each users' secure servers and not downloaded to external devices, including laptops. The information, even if de-identified, will be destroyed at the expiration of the project.

## **19. Economic Burden to Participants**

There will be no costs to participants that enroll this study.

## 20. Consent Process

Consent of participants will take place during their scheduled study visit. The research coordinator will first introduce the study to the participant and give the participant ample time to consider enrolling in the study and to ask questions. The subject will receive a copy of their signed consent form.

## 21. Setting

Study participants will be recruited with the help of study flyers. After participants have been screened based on inclusion and exclusion criteria and informed consent obtained, their study visit will take place in a designated research room located on the first floor of Emory Children's Center. Study samples that are collected will then be taken to the research lab for sample processing.

## 22. Pilocarpine Microneedle Patch Composition

The pilocarpine-loaded MN patches are fabricated by a two-step molding process using polydimethylsiloxane (PDMS) molds with some modification on an established method. The first casting solution is a mixture of 10% (w/v) pilocarpine nitrate, 10% (w/v) poly (vinyl alcohol) and 5% (w/v) sucrose, which is prepared by mixing the different components in water at the desired ratio. While this is our current formulation, we will investigate other formulations that can increase the pilocarpine content (on a solids basis) and thereby increase the dose of pilocarpine per MN. This solution is then cast on PDMS molds under vacuum to facilitate filling the solution into the molds.

After 20 min, excess solution is removed, and the filled molds are centrifuged at 5000 rpm for 20 min to dry the drug loaded MNs. The second casting solution containing 20% (w/w) polystyrene in 1, 4-dioxane is then cast on the filled PDMS molds under vacuum. The mold is kept under vacuum for another 3 h to dry the solution at room temperature, and then further dried at 40°C overnight before demolding the MN patches by adhesive tape. Each patch is immediately stored with desiccant in individual sealed pouches prior until use.

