#### Clinically used doses of Pilocarpine (Source: Lexicomp)

##### A. Pill Form

###### **Xerostomia:** Oral:

*Associated with head and neck cancer:* Initial: 5 mg 3 times daily; may titrate dose based on response and tolerability; usual dosage range: 15 to 30 mg/day; maximum: 10 mg/dose

*Sjögren syndrome:* 5 mg 4 times daily

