**Figure 4: Study Design Flowchart**

If there are any safety concerns reported by the DSMB, then these will be addressed by the study team with an appropriate modification of the study design or intervention. This will be followed by submission of an amended study protocol to the IRB to reflect the changes made to the study protocol. After approval of the amended study protocol, the study team will conduct the revised testing procedure on 10 subjects and submit safety data to the DSMB again for their review and approval.

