healthy subjects only. The results of this study will compare the effectiveness of the microneedle method of sweat induction with the standard of care pilocarpine iontophoresis method in human subjects and will not change the labeling of the drug. The sweat collection phase and analysis of chloride concentration will remain in the same and we will simply compare the volume of sweat collected between the standard method of sweat induction (using iontophoresis) with our proposed microneedle-based approach.

- 3) In the case of a prescription drug, the investigation is not intended to support a significant change in the advertising for the drug.

This study and the data being collected from it will not be used in any advertising materials for the drug. The same drug (pilocarpine) is being used for sweat stimulation in this study and we are simply comparing the effectiveness of another mode of delivery of this medication. If found effective, it will not change the use of this drug for the purpose of sweat testing.

- 4) The investigation does not involve a route of administration, dose, patient population, or other factor that significantly increases the risk (or decreases the acceptability of the risk) associated with the use of the drug product (21 CFR 312.2(b)(1)(iii)).

The delivery of pilocarpine for sweat induction using the microneedle approach does not change the route of administration (transcutaneous) for the purpose of sweat testing. The dose used in microneedles is significantly lower and does not increase the risk for the subjects being tested. The patient population that this test is applicable to remains the same – all subjects that are being evaluated for Cystic Fibrosis. There is no change in the risk profile, as the drug is being applied to the skin for the stimulation of the sweat glands on the forearm. Since our proposed microneedle method does not involve the use of electric current, there will actually be a lower risk of tingling sensations and rarely skin burns that sometimes occur with the iontophoresis procedure. The standard pilocarpine iontophoresis method of sweat induction has been rarely reported to cause small burns on the skin surface related to the use of electric current. Our proposed method eliminates this risk of burns completely.

In particular, the FDA advisory document (page 5) provides the following explanation regarding the risk of the modifications made in the proposed study:

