The pilocarpine microneedles that will be used for the experimental procedure will be manufactured at Global Center for Medical Innovation (GCMI). This is not part of Georgia Tech. It is an independent institution. The pilocarpine-loaded MN patches are fabricated by a two-step molding process using polydimethylsiloxane (PDMS) molds with some modification on an established method. The first casting solution is a mixture of 10% (w/v) pilocarpine nitrate, 10% (w/v) poly (vinyl alcohol) and 5% (w/v) sucrose, which is prepared by mixing the different components in water at the desired ratio. This solution is then cast on PDMS molds under vacuum to facilitate filling the solution into the molds. After 20 min, excess solution is removed, and the filled molds are centrifuged at 5000 rpm for 20 min to dry the drug loaded MNs. The second casting solution containing 20% (w/w) polystyrene in 1, 4-dioxane is then cast on the filled PDMS molds under vacuum. The mold is kept under vacuum for another 3 h to dry the solution at room temperature, and then further dried at 40°C overnight before demolding the MN patches by adhesive tape. Each patch is immediately stored with desiccant in individual sealed pouches prior until use.

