## 23. Pilocarpine Microneedle Patch Manufacturing and Characterization

The steps involved in Microneedle patch manufacturing have been outlined in Appendix 01.

The device master record showing all the components that went into the research article is included in Appendix 2. Design Trace matrix is an engineering description of each feature of the microneedle patch and the respective rational for that feature is provided in Appendix 3.

Verification Testing for the research articles was done through several methods. A Mechanical Test Report is included in Appendix 4. Pig skin test report is included in Appendix 5. Process validation report is included in Appendix 6. A visual and dimensional analysis of the microneedle patch is included in Appendix 7.

The process of extraction of Pilocarpine Nitrate through HPLC method is described in Appendix 8.

A detailed drawing of the research article with all the measurements is included in Appendix 9.

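### Does the remark in Section 22 about higher-dose formulations mean the patch could change during the 50-subject study?

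*Combined protocol and SAP*

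**What the plan says.** Two sections describe the composition of the patch. Section 7, under the procedures for this study, states: "The first casting solution is a mixture of 10% (w/v) pilocarpine nitrate, 10% (w/v) poly (vinyl alcohol) and 5% (w/v) sucrose". Section 22 repeats the same mix, labels it the current one, and adds that "we will investigate other formulations that can increase the pilocarpine content (on a solids basis) and thereby increase the dose of pilocarpine per MN". The text after that remark goes back to casting the stated mix.

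Two sections rely on the dose being low. Section 6, arguing for the IND exemption, says: "The dose used in microneedles is significantly lower and does not increase the risk for the subjects being tested". Section 15 supports its statement about systemic side effects by saying that "the total dose of pilocarpine in each microneedle patch is less than 10% (one-tenth) of the standard adult dose", and refers back to the dose list in Section 3. The adult oral entry there for dry mouth associated with head and neck cancer reads "Initial: 5 mg 3 times daily; may titrate dose based on response and tolerability; usual dosage range: 15 to 30 mg/day; maximum: 10 mg/dose".

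On changes to the intervention, Section 4 (text with Figure 4) says: "If there are any safety concerns reported by the DSMB, then these will be addressed by the study team with an appropriate modification". An amended protocol follows, after which, as Section 15 repeats, "the study team will conduct the revised testing procedure on 10 subjects and submit safety data to the DSMB again". Separately, Sections 4 and 15 schedule a DSMB review at the end of the study, and Section 15 sends unforeseen side effects of the patch to the DSMB.

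Section 23 describes verification testing as complete and says: "The device master record showing all the components that went into the research article is included in Appendix 2".

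**The concern.** The remark stands in the section that defines the study patch, and nothing places the work outside the protocol. A reader can take it to mean that a stronger patch might be introduced between the first 10 subjects and the remaining 40. Three things would then be at stake.

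- **Safety premise.** The dose statements in Sections 6 and 15, and the first DSMB review, would have been made for a different patch. The amendment and repeat 10-subject review are triggered by a DSMB concern. A formulation change made by the study team has no review step of its own.
- **Comparison with iontophoresis.** Volume and chloride results from two versions could be pooled into a mean difference that describes neither.
- **Delivered dose.** Section 24 works from the drug left in the used patch, so the calculation needs that patch's starting load. The protocol text does not mention recording lot or version for each subject.

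**Working it through.** **The plan's own figures.** The enrolment split adds up: 10 + 40 = 50. The statement that patch content is below 10% of the standard adult dose cannot be reproduced, because the available text gives no patch load in mg. One-tenth of 5 mg is 0.5 mg; one-tenth of the 10 mg per-dose maximum is 1.0 mg.

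**How far a richer mix could move the dose.** From Sections 7 and 22, the drug's share of the listed solids is 10/(10 + 10 + 5) = 0.40. Assume the same dry mass per needle and the same number of needles per patch. Both are needed, because Section 22 speaks of dose per needle and Section 15 of dose per patch. The shares of 50% and 60% are illustrative.

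| Drug share of solids | Load factor | Current load must be below, for the 10% statement to survive | Against 5 mg | Against 10 mg |
|---|---|---|---|---|
| 50% | 0.50/0.40 = 1.25 | 10%/1.25 = 8% | 0.40 mg | 0.80 mg |
| 60% | 0.60/0.40 = 1.5 | 10%/1.5 = 6.7% | 0.33 mg | 0.67 mg |

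The ceiling is 1/0.40 = 2.5-fold. The statement in Section 15 therefore would not carry over automatically to a richer patch.

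**Pooling.** With k of 50 subjects on an earlier version, the pooled mean difference departs from the later version's by (k/50) × gap. For k = 10, 25 and 40 that is 20%, 50% and 80% of the gap. The size of the gap is unknown, and the documents suggest no change point.

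**Delivered dose.** Let f be the load factor and r the share of drug left in the patch. If the old load were used by mistake, the relative understatement is (f − 1)/(f(1 − r)). Taking r between 0.2 and 0.5 as an assumption:

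- f = 1.25: 0.25/(1.25 × 0.8) = 25%, up to 0.25/(1.25 × 0.5) = 40%.
- f = 1.5: 0.5/(1.5 × 0.8) = 42%, up to 0.5/(1.5 × 0.5) = 67%.

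**The plan as written.** Section 7 introduces its single composition as that of the microneedles for the experimental procedure. Section 22 gives the identical mix. Section 23 treats the article as characterised and verified, with a device master record, process validation report and detailed drawing among the listed appendices. No section assigns a second formulation to a subject. So k = 0 and f = 1: the pooling shift is (0/50) × gap = 0, the assay error is (1 − 1)/(1 − r) = 0, and the dose statements refer to the patch actually used.

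**The case for a change.** The strongest case for a change is that Section 22 really is silent on where the formulation work takes place, and that one sentence and a few data fields would settle the matter cheaply. The arithmetic is right on its assumptions. It is also true that no DSMB step is tied to a formulation change as such: neither the end-of-study review nor the review of unforeseen side effects would be set off by one.

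What stands is an ambiguity of wording. It does not amount to a defect, for four reasons.

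- Every harm begins with an event that the plan does not provide for.
- The study is not without oversight for such an event. Under criterion 5 of Section 6 the study commits to IRB review and to following the applicable rules. Criterion 4 makes it a condition of the exemption that the dose does not significantly increase risk.
- Starting loads, lot records and further review rules may be in the manufacturing, device-record, process-validation and assay appendices or in the DSMB charter. These are listed in Section 25 but were not available, so silence in the main text is weak evidence that they are absent.
- Delivered dose is not one of the two outcome measures in Section 5. An assay error would leave the volume and chloride comparisons untouched.

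An advance rule that bases the main comparison on the final version only is no clear gain either. With 10 subjects left, the 95% confidence interval for the mean paired difference has half-width 0.715 SD, against 0.284 SD with 50, which is 2.52 times wider.

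**Conclusion.** No change to the plan follows. The remark in Section 22 is best read as a note on continuing product development, placed in a section that otherwise describes a fixed patch. On that reading the comparison with iontophoresis is unaffected, with a shift of zero. The shifts of 20% to 80% of the between-version gap, and the dose thresholds of 8% and 6.7%, matter only if another formulation is given to subjects.

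The conclusion rests on one assumption, which Sections 7 and 23 support but do not state outright: one formulation serves all 50 subjects. If the sponsor did bring in another, Sections 6, 7, 15 and 22 would have to be reconciled at that point, and an analyst would report volume and chloride by version as a matter of course. No view is taken here on which formulation, dose or review rule is right.
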